MOUD Treatment Retention. Treatment retention will be operationalized as a composite of medication adherence (number of weeks buprenorphine or methadone present in the urine toxicology report) and treatment adherence (number of weeks attended required counseling as part of comprehensive treatment as usual, as indicated in clinical notes) - throughout the prenatal period to 3 months postpartum.

Opioid use abstinence. Weekly point of care urine toxicology screening is conducted as part of standard care with all MOUD patients at partner practices to assess for THC, cocaine, benzodiazepines, methamphetamine, opioids, methadone and buprenorphine. Opioid abstinence will be measured as number of weeks consistently abstinent from opioids over the perinatal period to 3 months postpartum.

Secondary End Points:

Other substance use. Other substance use will be measured as number of weeks the participant used marijuana and/or other drugs as indicated in urine toxicology reports. Tobacco and alcohol use will be measured by way of documentation in clinical notes from visits.

Participant Self-Report Procedures: Participants will complete secured online survey assessments at baseline, post-intervention, and 3-months postpartum. The project coordinator will ensure that participants receive the assessment surveys at the specified times in the manner preferred by the participant. If participants wish to receive the survey via email, the survey will be sent as a unique study-identified password-protected link. The project coordinator will monitor and track survey assessment completion and ensure that participants receive gift card incentives for survey completion in a timely manner. For participants who do not wish to complete the survey online, the project coordinator will arrange for either a phone interview with the participant to complete the survey or will mail the participant the survey along with a self-addressed and stamped envelope for the participant to return the survey. The assessment survey will include the following:

Primary End Points:

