9.2 Sample Size and Randomization

Sample Size.

Aim 1: For the longitudinal models of binary outcomes (abstinence, retention), assuming a within-person correlation of 0.5, there will be 80% power to detect difference between arms in the proportion retained at the 3 timepoints if the average percentage retained in the TAU arm is 60%, and the average percentage retained in the MMORE arm is 79.2%. Similar power is obtained if the TAU arm has a retention percentage of 70% while the MMORE arm has a percentage of 87% across the three timepoints. In terms of comparing abstinence longitudinally, there will be 80% power to detect a difference between arms in the percentage abstinent at the 3 timepoints if the average percentage abstinent in the TAU arm is 80% while in the MMORE arm is 94%. Power for the comparison of number of weeks abstinent during the 8-week intervention period will be 80% (at the two-sided 0.05 significance level) for differences between arms that are 0.52 times a standard deviation or more. Analyses testing for differences between arms in changes between baseline and 8-weeks, will have 80% power to detect differences that are 0.40, 0.52, and 0.61 times a standard deviation, assuming within-person correlations of 0.7, 0.5, and 0.3, respectively. We will aim to recruit 150 participants to allow for attrition (20%).

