10. DATA COLLECTION AND QUALITY ASSURANCE

10.1 Data Collection Forms

Opioid abstinence and MOUD treatment retention will be collected by way of medical chart data extraction and self-report by consented participants.

Secondary outcomes will be collected by way of self-report by consented participants through completion of assessment surveys.

Case Report data collection forms have been created for the following:

- Participant Demographics and physical conditions at baseline
- Session Events Form
- Intervention Experience Form
- Weekly Monitoring Form
- Adverse Events
- Clinical Record Data Collection Template
- Self-Report Assessment Battery (SRAB)

The SRAB has been programmed in secured, password protected HIPAA compliant online survey software (Dartmouth College REDCap). Individual participant survey links will correspond to the unique participant study ID so that all pages of each assessment survey (and corresponding database) will be linked to the participant.

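### The chart measure of other substance use counts drug-positive weeks with no denominator for weeks tested, so better retention in the MMORE arm biases it upward and can mask or reverse a true reduction

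*Combined protocol and SAP*

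**What the plan says.** Section 6.2, under the clinical record indicators, lists this secondary endpoint: "Other substance use will be measured as number of weeks the participant used marijuana and/or other drugs as indicated in urine toxicology reports". The source of those reports is given just above it: "Weekly point of care urine toxicology screening is conducted as part of standard care with all MOUD patients at partner practices". The document describes no urine collection run by the study itself. The medication part of the primary retention endpoint is read from the same reports, as "number of weeks buprenorphine or methadone present in the urine toxicology report".

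Retention is expected to differ by arm. Section 9.2 takes 80% power "if the average percentage retained in the TAU arm is 60%, and the average percentage retained in the MMORE arm is 79.2" per cent, and adds: "Similar power is obtained if the TAU arm has a retention percentage of 70% while the MMORE arm has a percentage of 87" per cent.

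Other parts of the document describe this outcome differently. Section 9.5.2 defines other substance use by the self-reported ASSIST only. Section 10.1 says: "Secondary outcomes will be collected by way of self-report by consented participants through completion of assessment surveys". Section 10.1 nevertheless lists a clinical record template among its forms. Section 9.6 names no analysis for other substance use, and the plan contains no missing-data method.

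**The concern.** A count of positive weeks is a rate of use multiplied by the number of weeks in which use could be detected. A woman who leaves MOUD care is no longer screened at the practice. On a literal reading of the definition, her later weeks contribute nothing, whatever she is using. If MMORE keeps more women in care, its participants have more weeks in which a positive result can be recorded. The primary benefit of the intervention then feeds into a secondary endpoint in the unfavourable direction: a true fall in use is understated and, if small enough, appears as a rise. Readers may give the urine count extra weight because it looks objective next to self-report.

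**Working it through.** **Reproducing the plan's retention figure.** Inputs from section 9.2: "assuming a within-person correlation of 0.5, there will be 80% power to detect difference between arms in the proportion retained at the 3 timepoints"; 150 recruited less 20% gives 120, or 60 per arm. The level "at the two-sided 0.05 significance level" is stated there for weeks abstinent and is assumed here for retention.

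- Effective n per arm = 60 / [(1 + (3 − 1) × 0.5)/3] = 90.
- Pooled standard error = √(2 × 0.696 × 0.304/90) = 0.0686; unpooled = √((0.60 × 0.40 + 0.792 × 0.208)/90) = 0.0671.
- Power = Φ[(0.192 − 1.96 × 0.0686)/0.0671] = 80.5%. The 70% vs 87% pair gives 79.8%.

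The planned retention gap is therefore taken as the plan states it. The plan gives no figure for other substance use.

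**Expected count.** Positive weeks = tested weeks × weekly probability of a positive urine. At equal weekly use, that probability cancels from the ratio between arms, leaving the ratio of tested weeks. The break-even is the relative fall in weekly use at which the MMORE count equals the TAU count: 1 − 1/ratio.

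Follow-up length is not given. I assume 26 to 28 weeks, from recruitment in the second or early third trimester to 3 months postpartum. If a share p is retained at the end and losses fall evenly over the last L of W weeks, mean tested weeks = (W − L) + L(1 + p)/2. Under a constant hazard over W weeks, it is W(1 − p)/(−ln p).

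| Reading of 60% vs 79.2% | TAU weeks | MMORE weeks | Ratio | Break-even |
|---|---|---|---|---|
| Share of 28 weeks observed | 16.8 | 22.2 | 1.32 | 24% |
| Retained at end, even loss over 28 weeks | 22.4 | 25.1 | 1.12 | 11% |
| Retained at end, constant hazard over 26 weeks | 20.4 | 23.2 | 1.14 | 12% |
| Retained at end, loss in last 12 of 28 weeks | 25.6 | 26.75 | 1.045 | 4% |
| Retained at end, loss in last 7 of 26 weeks | 24.6 | 25.27 | 1.027 | 3% |

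The last two rows follow section 2.1, which reports 40% discontinuation by 3 months postpartum in a New Hampshire programme, with the steepest loss between 6 weeks and 3 months (about 13 − 6 = 7 weeks). Over 24 to 32 weeks of follow-up, the 12-week row ranges from 5.3% (22.752/21.6) to 3.9% (30.752/29.6), and the 7-week row from 3.0% (23.272/22.6) to 2.2% (31.272/30.6). For 70% vs 87%, the ratios are 1.24 (share of weeks), 1.10 (even loss over 28 weeks) and 1.04 (last 12 weeks).

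**In weeks.** With an assumed 30% weekly positivity in both arms and 28 weeks:

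- Share of weeks: 16.8 × 0.30 = 5.04 vs 22.176 × 0.30 = 6.65 (+1.61).
- Even loss: 6.72 vs 7.53 (+0.81).
- Last 12 weeks: 7.68 vs 8.03 (+0.35).

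Positive tests divided by tests performed give 30% vs 30% in every case.

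**Simulation (illustrative).** 60 per arm, 28 weeks, Wilcoxon test, assumed variation between women. Figures are in the order share of weeks, even loss, last 12 weeks.

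- Equal 30% use: MMORE mean count higher in 92%, 72% and 60% of trials; significantly higher in 26%, 10% and 4%, where 2.5% is nominal for one direction.
- MMORE use cut to 21% (a 30% reduction): MMORE mean count higher in 36%, 12% and 5%; significantly lower in only 9%, 28% and 44%.

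**The case against.** A reader might infer that if MMORE improves retention it will appear to increase drug use. The documents do not support that. It holds in expectation only if weekly use falls by less than the break-even, which is 3 to 24% depending on the reading. MMORE is meant to reduce use, so the net sign is open.

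A reader might also take 32% as the expected size. Section 9.2 speaks of an average over three assessment points, not a share of weeks, and the late drop-off in section 2.1 points to the low end. With loss confined to the last 7 to 12 of 26 weeks, simulated two-sided false-positive rates under equal use were 5 to 8%, close to nominal. In any case, the Wilcoxon test is not the plan's choice here: section 9.6 offers a t-test or Wilcoxon for weeks retained and nothing for this outcome.

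Nor does the plan say that untested weeks score as no use. That follows from a literal reading of a definition with no missing-urine rule, and the silence is the defect.

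Finally, sections 9.5.2 and 10.1 point to ASSIST, so the chart count may be only supplementary. That limits the consequence. It does not remove it, because 6.2 lists the chart count as a secondary endpoint and nothing says which source governs.

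**Conclusion.** The concern holds as a bias in one version of a secondary endpoint. As defined, the chart count depends on time under testing, and the planned retention gap pushes it upward in the MMORE arm. The direction is the same under every reading examined. The size ranges from slight, if dropout is late, to material, if the planned percentages describe weeks observed. The ratios rest on the plan's retention figures together with assumed follow-up length and dropout timing. The week counts and simulations also rest on assumed positivity, and the simulations on assumed variation between women. The documents support neither a predicted false harm signal nor a specific inflated error rate. A correction before analysis is worthwhile, but it is not critical to the trial's main conclusions.

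**What to change.** 1. Define the chart endpoint as positive tests out of tests performed, from randomisation to a fixed end such as 3 months postpartum. Use a binomial model allowing for extra variation between women, or a count model with log number of tests as offset.
2. Report tests performed per woman by arm.
3. State how weeks without a urine are handled, and add a sensitivity analysis that varies the assumed use in those weeks. The rate removes the mechanical bias but still describes only women in care.
4. Reconcile 6.2 with 9.5.2 and 10.1 on which source governs. ASSIST is collected whether or not a woman is in care, so it avoids this mechanism, although survey non-response remains. Making it the main measure is a judgement, not an obvious correction: 6.2 itself warns that fear of child protective involvement complicates self-report here, before arguing that well-run studies can obtain reliable answers. If ASSIST governs, acknowledge that caveat and settle its follow-up recall period, which 6.2 sets as the time since the previous survey and 9.5.2 as the preceding three months.

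The cost is SAP wording. The number of tests should come from the chart review already planned, with no added burden on participants.

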3. STUDY DESIGN

Activities to meet Aim 1. We will evaluate MMORE in a two-group randomized controlled design comparing treatment as usual (TAU) in partner maternity care practices with TAU + MMORE.

Participants will be 150 English-speaking consenting pregnant women aged 18 years and over who have a confirmed singleton pregnancy and are receiving perinatal services and medication for opioid use disorder at partner maternity care practices. We will aim to recruit women in their 2nd/early 3rd trimester of pregnancy.

After completion of the baseline assessment, consented participants will be randomly assigned to participate in the 8-session virtual yoga-mindfulness group intervention or to receive TAU only.

All intervention participants will be provided with a unique password-protected access link to the digital support materials, as well as detailed instructions for how to access the materials. A unique study code will allow us to monitor individual participant use of the support modules for analytic purposes.

All consented participants will complete assessments at baseline, post-intervention (8 weeks for TAU participants) and 3 months postpartum. Participants will complete assessments via a secured, de-identified and password-protected link accessed either on a study-provided laptop computer at a scheduled practice visit or via a protected email link to the user for completion at home or on another secure device with Internet access. Assessments will take approximately 20 minutes to complete. Based on formative data from phase 1 of this project, and other work the research team has conducted with the target population, we anticipate most women will have some access to the Internet either via a mobile phone, tablet, or home computer. If a participant cannot complete an assessment online, a paper version will be provided. The study staff will track ways that participants complete assessments. Participants will receive local gift cards for completion of each assessment.

Activities to meet Aim 2. All study participants (TAU and TAU+MMORE) will complete brief mobile assessments at the end of each week of their assigned cohort period. Assessments will be completed using either a mobile device or computer. Participants will receive a prompt (near end of the week) to complete the assessment. The encrypted, password-protected weekly brief assessment will include items to assess the following:

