Treatment Retention. Self-reported adherence to medication for opioid use disorder will be assessed by an adaptation of items from the well-established Adherence to Medication questionnaire originally developed for assessing adherence to antiviral medications among persons with HIV/AIDS. (i.e., when was the last time you skipped buprenorphine medication? [past 2 days, within the past 2 weeks, 2-4 weeks ago, 1-3 months ago, never skipped past 3 months]. Participants will also report how often they attended group/individual counseling in the past 3 months [every week, every other week, once a month, less than once a month].

Opioid abstinence. The reliability of self-report of substance use for pregnant and parenting women is especially complicated due to well-founded fears of child protective service involvement and potential loss of children. That said, when research studies are well-conducted and assurances for protection of participant privacy are clear and conveyed with messaging informed by community partners with lived experience, women do reliably self-report their use behaviors.

Opioid use will be assessed with relevant items from the Alcohol, Smoking and Substance Involvement Screening Test, aligned with relevant timeframes (baseline: past 6 months, post-intervention and 3 month postpartum: past 3 months). Opioid use disorder severity will be assessed with items corresponding to DSM-V diagnostic criteria.

Secondary End Points:

Other substance use:

Self-reported frequency and quantity of opioid and other substance use (including alcohol, marijuana, and tobacco) will be assessed with the Alcohol, Smoking and Substance Involvement Screening Test, aligned with relevant timeframes (baseline: past 6 months, post-intervention, 3 month postpartum: since last survey).

Mental Health:

Depression will be assessed using the Edinburgh Prenatal and Postnatal Depression Scales, both of which have been used extensively with the target population.

Anxiety will be assessed with the Generalized Anxiety Disorder Scale (GAD-7)², a psychometrically sound instrument routinely used in general health care settings.

Stress will be assessed with the Perceived Stress Scale,³ a psychometrically sound instrument that has been used in other studies of contemplative interventions with pregnant women⁴⁻⁷.

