6.2.2 Enrollment, Baseline, and/or Randomization

Enrollment

In this study, the enrollment date will be the date that all of the screening criteria were met, and the individual consents to participate.

Baseline Assessments

Participants will complete the baseline assessment upon consenting to participate in the study. The project coordinators will administer the baseline assessment to the participant through a secure online survey. For participants who do not wish to complete the survey online, the project coordinator will arrange for either a phone interview with the participant to complete the survey or will mail the participant the survey along with a self-addressed and stamped envelope for the participant to return the survey. Both forms of the assessment will be coded with a unique study ID.

Randomization

Following baseline completion, participants will be randomized to condition by the lead project coordinator. The lead project coordinator will meet via phone with participants assigned to the MMORE condition to explain the condition. Participants in the MMORE condition will receive a secure password-protected access to the digital companion features.

Randomization will be conducted via permuted blocks. Once 8-10 participants have enrolled, an intervention will commence for that cohort. The randomization block size would be random, with blocks of size 4, 6, and 8. In thinking about how best to implement our group randomization plan in the context of the reality of recruitment of this high-risk target population, we have developed a plan of ongoing recruitment and starting a new group at least every 8 weeks. With a conservative recruitment

rate of 12 participants per month, we do not anticipate a good deal of differential lag-time between recruitment into the study, completion of baseline, randomization, and start of a new group.

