6.2.3 Blinding

The study will be blind to the Principal Investigator, the statistician, and to those on the team responsible for participant data collection. We will work to try to blind clinicians delivering TAU to participant assignment but there is a chance that patients will reveal their condition to clinicians despite our best efforts. To achieve blindness, treatment assignment will be done by the lead project coordinator, who will not be directly involved in evaluation or data collection. Survey data collection will be conducted by the project coordinator who will be blinded to participant treatment assignment. Participant self-report surveys will be implemented using secured online survey software, which will significantly limit the potential of the project coordinator to introduce bias.

Stakeholder	Blind Status	Involved in Data Collection?	Steps to ensure blindness
TAU Clinicians	Potentially un-blinded	No	Patient participants may indicate to their clinician that participating in study. Clinicians will be instructed not to specifically ask patients about study.
PI	Blinded	No	The PI will not be involved in the group assignment or collection of data; analyses will be conducted when data are unlocked.
Statistician	Blinded	No • Will conduct analyses	Will not have access to randomization algorithm key
Project Coordinator	Blinded, with possibility of being inadvertently un-blinded	Yes	
 Will be instructed not to inquire with participants about study. Will report instances of learning status Assessments conducted via secured online survey software.
Lead project coordinator	Un-blinded • Knows random assignment • Introduces participants to their treatment condition	No	

	
 • Prepares necessary reports 		
--	--	--	--

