6.2.4 Contamination

Since the study is not necessarily blind to participants, we will take steps to evaluate potential contamination with regard to the intervention by way of communication among women who may receive services in the same setting. It is possible that participants that receive MMORE will interact with women in the TAU only group through the partner practice and communicate about the intervention. While it is unlikely that communication will convey substantive information to influence results, we will evaluate extent of potential contamination by including questions about communication with others about the intervention in the post-intervention assessment battery (e.g. Did you talk with other women in the study? What information conveyed? What information learned?).

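### Follow-up surveys may be done by phone interview, which removes, for those surveys, the online self-completion that section 6.2.3 relies on to limit interviewer bias

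*Combined protocol and SAP*

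**What the plan says.** Section 6.2.3 (Blinding) gives survey collection to a project coordinator blinded to assignment and relies on the survey mode: "Participant self-report surveys will be implemented using secured online survey software, which will significantly limit the potential of the project coordinator to introduce bias". The table in that section repeats online completion as a step that keeps the coordinator blind. It also says that coordinators are told not to ask about the study and are to report any assignment they learn, and it accepts that inadvertent unblinding may happen. Neither text nor table mentions phone or mail.

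Section 6.2 (Participant Self-Report Procedures) does provide for other modes. If a woman prefers not to answer online, "the project coordinator will arrange for either a phone interview with the participant to complete the survey". The other choice there is a posted questionnaire with a prepaid return envelope. Section 6.2.2 repeats both options for baseline, where "Participants will complete the baseline assessment upon consenting to participate in the study" and randomisation follows. Section 3 mentions only paper: "If a participant cannot complete an assessment online, a paper version will be provided". It adds that staff will track how each assessment is completed.

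Two parts of the survey matter here. Section 6.2.4 measures contamination by "including questions about communication with others about the intervention in the post-intervention assessment battery", with examples asking whether the woman talked with others in the study and what was passed on or learned. Section 6.2 places self-reported medication adherence and opioid use under primary end points, and calls the reliability of such self-report "especially complicated due to well-founded fears of child protective service involvement and potential loss of children". It goes on to say that women do report reliably when privacy protections are clear and well conveyed.

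**The concern.** The safeguard in 6.2.3 works because nobody hears the answers. A phone interview puts a listener back, and two things follow.

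First, at the post-intervention survey the script itself asks about the intervention. A woman who describes what she told others about the sessions has in effect stated her arm. An instruction not to inquire cannot help when the inquiry is a survey item. If that interviewer then collects the 3-month postpartum survey, it is no longer collected blind.

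Second, answers about opioid use and skipped medication are spoken to study staff, in a population whose fear of disclosure the protocol itself records. If disclosure is lower by phone, self-reported use is understated. If phone use also differs between arms after randomisation, the comparison is biased. Such a difference is conceivable, since section 5.1 ties tablets, hotspots and videoconferencing training to the intervention arm, but the documents do not predict one.

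The measures exposed are the self-report versions of the two primary endpoints and the self-reported secondary outcomes (depression, anxiety, stress, posttraumatic stress, mindfulness, quality of life, pain).

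**Working it through.** **1. Sections side by side.**

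| Section | Ways of answering | Who it covers |
|---|---|---|
| 3 | online; paper | women who cannot answer online |
| 6.2 | online; phone interview; mail | women who do not wish to answer online, any survey |
| 6.2.2 | online; phone interview; mail | the same, at baseline |
| 6.2.3 | online only | all surveys, no exception |

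Section 6.2.3 does not account for the phone route. Section 3 differs from 6.2 in the reason (cannot versus does not wish) and omits phone; it is incomplete rather than flatly contradictory.

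**2. Which surveys are exposed to which problem.**

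| Survey | Before or after randomisation | Can the call reveal the arm? | Disclosure concern |
|---|---|---|---|
| Baseline | before | no, there is no arm yet | yes |
| Post-intervention | after | yes, through the contamination questions | yes |
| 3 months postpartum | after | the arm may already be known | yes |

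**3. Who the interviewer is.** Section 6.2 says the coordinator arranges the call and does not say who conducts it. Section 6.2.3 gives survey collection to the project coordinator, so a coordinator is the likely interviewer. Sections 6.2.1 and 6.2.2 speak of coordinators in the plural, and nothing assigns one to each woman. The same person may therefore return at 3 months, but need not.

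**4. Size.** The documents give neither the share answering by phone nor the disclosure rate by mode. What follows is an illustration that applies only if self-report is the analysed source.

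The plan's own figure first (section 9.2): abstinence 80% vs 94%, correlation 0.5, three time points, 150 × (1 − 0.20) = 120 analysed, 60 per arm. Design effect = (1 + 2 × 0.5)/3 = 0.667; effective n = 60/0.667 = 90 per arm. With mean proportion 0.87, SE under the null = √(0.87 × 0.13 × 2/90) = 0.0501 and SE under the alternative = √((0.80 × 0.20 + 0.94 × 0.06)/90) = 0.0490. Power = Φ((0.14 − 1.96 × 0.0501)/0.0490) = 80.3%, matching the stated 80%.

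Now let observed use = true use × [1 − s(1 − d)], where s is the phone share and d is disclosure by phone relative to self-completion. Assume d = 0.5 to 0.8. True use is 20% (TAU) and 6% (MMORE).

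| Phone share TAU / MMORE (assumed) | Observed difference, points | Power | False difference if true use is 20% in both arms |
|---|---|---|---|
| 0% / 0% | 14.0 | 80.3% | 0 |
| 10% / 10% | 13.3 to 13.7 | 78 to 79% | 0 |
| 25% / 25% | 12.3 to 13.3 | 74 to 78% | 0 |
| 40% / 10% | 10.3 to 12.5 | 60 to 73% | 1.2 to 3.0 points against MMORE |

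Example, 40%/10% with d = 0.5: TAU 0.20 × (1 − 0.40 × 0.5) = 0.160; MMORE 0.06 × (1 − 0.10 × 0.5) = 0.057; difference 10.3 points. Reversing the split reverses the sign of the false difference.

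The calculation treats all three time points alike, as the plan's power statement does. The arm-specific split is conceivable only at follow-up, and section 9.6 evaluates the outcomes at 8 weeks and 3 months postpartum.

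**The case against.** The strongest reply is that this is a minor route with other protections around it. Online is the default, and a woman who declines it can take the mailed survey, which has no interviewer. Coordinators are told not to inquire and must report any assignment they learn, and the plan openly accepts some unblinding. Section 6.2 also holds that women report reliably under clear privacy assurances, and a Certificate of Confidentiality is in place (sections 7.1 and 11.3). Nothing in the documents says disclosure is lower by phone. Both primary endpoints also have chart definitions, from weekly urine toxicology and counselling notes, which survey mode cannot touch. Banning phone calls would exchange an unmeasured reporting bias for missing data, in a trial that already allows for 20% attrition.

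Most of this stands, and it rules out several stronger readings that a reader might infer:

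- That the phone option cancels the blinding safeguard. It removes it only for surveys completed by phone.
- That women speak to the very person who will survey them again. The documents do not say so.
- That mode is always chosen after randomisation. At baseline it is chosen before.
- That the primary result is biased. Section 10.1 draws abstinence and retention from both chart and self-report, and section 9.6 does not say which source the GEE models use.

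What does not stand is that the remaining instructions suffice. They do not cover arm-revealing questions that the survey itself asks.

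**Conclusion.** The concern holds in limited form. Section 6.2.3 relies without exception on a mode that 6.2 does not guarantee. For follow-up surveys done by phone, the contamination questions can reveal the arm, and sensitive answers are given to staff. Baseline calls raise only the disclosure concern, and chart and toxicology outcomes are untouched.

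The size is unknown. The table under the check shows it could be negligible (about 1 to 2 points of power at 10% phone in both arms) or material (power 60 to 73% with an uneven split), but every phone share and disclosure rate in it is assumed. It should not be read as an estimate. Whether the primary analysis is affected at all depends on which source feeds the GEE models. The self-reported secondary scales have no chart equivalent planned, so they are exposed either way. This is a cheap improvement the plan should make, not a flaw that undermines the trial.

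**What to change.** 1. In 6.2 and 6.2.2, offer self-completion first (link, study device or prepaid mail) and keep the phone interview as a last resort.
2. Take the 6.2.4 contamination questions out of any phone call. Send them as a separate self-completed form that the person collecting later surveys does not see.
3. When the rest of a survey is done by phone, have the substance-use and adherence items self-completed on paper or by link.
4. Use the completion mode already tracked under section 3: report it by arm and visit, and repeat the self-report analyses without phone-completed follow-up surveys.
5. Amend sections 3, 6.2, 6.2.2 and 6.2.3 so that they list the same modes and the blinding section covers each.

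Stating in 9.6 whether chart or self-report defines the GEE outcomes would also settle whether this reaches the primary result.

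The cost is protocol wording, one short separate form and one sensitivity analysis. The downside is slightly more missing self-report items among women who would answer only by phone; keeping the call as a last resort limits this. Excluding phone-completed surveys also drops a possibly selected group, so that analysis supplements the main one and does not replace it.
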